VR sessions will be reviewed as part of secondary analyses to qualitatively explore providers' language around addressing particular sources of hesitancy for HPV vaccination. Language will be assessed through thematic analysis and summative content analysis. For example, we will assess provider's responses to parental concerns regarding HPV vaccination prompting early sexual activity initiation. We will explore if race of the animated parent avatar influences providers' word choice. We will explore if baseline provider characteristics such as age, sex, and attending vs. resident status, year of residency impact language.

Transcripts from the VR simulations will be coded by a study team member to assess primary learning objectives. An artificial intelligence (AI) software from IBM, Watson, will be used to train the software through machine learning to process and code data to begin exploring the feasibility of adapting the VR simulation training to use AI instead of requiring a human facilitator. Watson is a password protected software (add URL). IBM Watson has been used in Medical Education research⁷⁹. The coded portions of the transcripts will be used as examples for Watson to create "intents." Intents are a collection of inputs, in our project they are the primary learning objectives, that Watson is taught to recognize. In this way, Watson recognizes that a participant intended to use a particular skill. A study team member will use the de-identified transcripts to train Watson, to recognize and code portions of transcripts from the VR simulations. Next, we will test Watson's coding against members of the research team's coded transcripts to test the inter-rater reliability between AI and study team members. The goal is to train Watson to accurately identify primary learning objectives as a first step in assessing the feasibility for an automated version of the VICTORI intervention.

Power considerations: Power considerations are provided for our primary aim and outcome of

determining whether VICTORI increases vaccine initiation. The PPCC is staffed by 80 residents and 20 attending physicians and reflects the maximum sample size for the intervention. To inform our power calculations for this proposal, we reviewed all PPCC patient visits for 11 to 17-year-old boys and girls from July 1, 2016 to June 30, 2017. HPV vaccination was initiated in 53% of visits for residents and 34% for attending physicians with greater between provider variation for residents. In addition, attending physicians saw more patients (n=9) in this age range on average per month than residents (n=2), and graphical analyses and formal regression modeling did not support material seasonal variation in initiation rates. Simulated outcomes based on these data were used to determine the minimum detectable odds ratio (OR) for vaccine initiation according to study period (i.e. pre- vs. post-intervention) as estimated from the proposed GLMER model. For resident and attending physicians combined, we assumed a total of 70 physicians having on average four patient encounters per month, a baseline probability of vaccine initiation of 43%, and a standard deviation for the subject-specific intercept of 0.55. Study power was determined to be 80% to detect an OR=1.5 based on 10k simulations. *This corresponds to a post-intervention vaccine initiation probability of 53%; or a 10% pre- to post-intervention difference.* Thus, conducting this intervention at CCHMC is expected to provide sufficient power to detect a clinically meaningful effect size for the response.

Potential Problems and Alternative Strategies: Insufficient recruitment may occur, but we do not anticipate this to be an issue as we have successfully conducted a VR intervention focused on flu vaccination with this population.²⁶ In addition, our team and expert consultants have provided extensive recommendations to recruit providers. There is the possibility of incomplete surveys; scale items with <25% missing data will be included in the analysis.⁷⁸ Multiple imputation and/or maximum likelihood estimation will be implemented should material missing values be realized for the survey responses and we will conduct a sensitivity analyses to determine the robustness of study findings to the assumptions of the imputation model.

Aim 3: Determine modifiable barriers related to HPV vaccine non-completion for future enhancement of VICTORI accordingly

Setting and Population: The PPCC is a busy, academic clinic in Hamilton County, Ohio with about 33,000 visits annually, serving 19,000 patients that are predominantly underserved with approximately 90% insured through Medicaid. Seventy-five percent of the patient population is African American and 5% is Latino. PPCC serves a population that is at high risk for HPV infection and its sequela, and therefore, we anticipate the findings to be generalizable to other urban primary care clinics that serve predominantly minority populations. Hopple Street Neighborhood Health Center (HSNHC) which served as a control during Aim 2, serves a similar population to the PPCC with 6000 unique patients and 13,000 patient visits per a year.

Design and Measures: We will first identify patients aged 9 to 17-year-old boys and girls who initiated the HPV vaccine series between 10/01/2020-06/01/2022 after seeing a provider who underwent VICTORI training. We will review social determinants of health screener of those who had not completed the HPV vaccine series by 14 months after initiation compared to those who did complete the HPV vaccine series. We will also collect demographic information (DOB, age, sex, race, ethnicity, health insurance; see appendix VICTORI Chart Review),

Based on these data, future revisions will be made to VICTORI to allow physicians to deliberately practice screening for and addressing barriers to vaccine series completion. Findings from this aim will provide

information to create a data-informed enhancement of VICTORI's simulated scenarios supporting series completion, which is critical to decreasing morbidity related to HPV-associated cancers.

Data Analysis and Sample Size Calculations:

- Review between n = 300 (minimum) – 720 (maximum) patient records
- These sample size calculations were derived from Peduzzi et al. {Peduzzi, 1996 #3012} guideline for the minimum number of cases to include for a logistic regression. The formula used for the calculation of the minimum number of participants was $N = 10 * 18 \text{ variables} / 60\%$ (the estimated proportion of patients who completed the HPV vaccine series). The formula used for the calculation of the maximum number of participants was $N = 10 * 18 \text{ variables} / 25\%$ (the estimated proportion of patients who completed the HPV vaccine within the recommended timeframe). As a note, we will also examine the proportion of patients who meet the guidelines for timely series completion (N = 400 minimum) using the following equation: $N = 10 * 18 \text{ variables} / 45\%$ (the estimated proportion of people who completed the HPV vaccine within the recommended timeframe).
- Descriptive analyses as well as data variance and distribution to characterize variables.
- Logistic regression to determine factors independently associated with completing the HPV vaccine series including: clinic location (PPC v Hopple), type of visits at first dose, resident v attending physician, provider sex, age of patient at first dose, patient sex, patient race, insurance at first dose, and social risk screener questions.

Required dose for vaccine series completion (2 doses v 3 doses) will also be included in the descriptive analyses

Training of Study Personnel

All staff will undergo training in maintaining confidentiality and have completed the required Collaborative Institutional Training Initiative (CITI) courses and research ethics classes as required by CCHMC and Cincinnati Children's Research Foundation.

Recruitment and Consent Procedure

Aim 1: Evaluate VICTORI for acceptability and feasibility

Before recruiting any participants, approval from the CCHMC IRB will be obtained. Physicians working in the CCHMC THC will be sent invitations to participate in the study via email. The email will explain the purpose of the study, what participation entails, data to be collected, reimbursement, and contact information for study personnel. Participants will also be recruited in person. Staff working in the CCHMC THC will be recruited in person with an informational flyer explaining the purpose of the study, what participation entails, data to be collected, reimbursement, and contact information for study personnel. THC staff will be consented as a group prior to engaging in the study. Written consent, as appropriate, will be obtained from all participants for their participation in this phase of the study.

PPCC staff will be consented as a group prior to engaging in VICTORI. Written consent will be obtained from each participant in accordance to CCHMC policy 41-1.4.

The physicians will be consented using REDCap e-consent. REDCap is a secure web application for building and managing online surveys and databases. While REDCap can be used to collect virtually any type of data (including 21 CFR Part 22, FISMA, and HIPAA-compliant environments), it is specifically geared to support online or offline data capture for research studies

and operations. The CCHMC REDCap team has templates available for research use for eConsenting which includes Consent to be a Research Subject and Authorization to Use or Disclose (Release) Health Information that Identifies You for a Research Study (HIPAA). The REDCap electronic consent format does not accommodate the current CCHMC formatting which includes headers with logos and stamps on each page and will therefore require some modifications. Participants will be sent a link to review and complete the e-consent on their own, however, study team contact information will be available for questions. CRC will verify e-consent completion, and sign that consent has been obtained within one business day of participant completion. Since the participants will complete the consent on their own, an informed consent process note will not be completed for physician participants.

Copies of consent forms for staff and physicians will not be submitted to Health Information Management, since these participants are not patients at CCHMC.

Aim 2: Conduct a single-site intervention assessing the efficacy of VICTORI in increasing HPV vaccine initiation and completion rates

Before recruiting any participants, approval from the CCHMC IRB will be obtained. Physicians and staff working in the CCHMC PPCC and attending physicians working in the HSNHC will be sent invitations to participate in the study via email three times over a four-week period. Participants will also be recruited in person. Physicians and staff will be recruited as they were in Aim 1.

Physicians at PPCC and HSNHC will be consented using e-consent. A waiver of documentation of informed consent is requested since no private identifiable health information will be collected and the purpose of the study is to evaluate the effectiveness of VICTORI to increase HPV vaccination rates in clinic. This also aligns with institutional guidelines for remote consenting due to social distancing dependent on the COVID-19 pandemic. A study information sheet will be provided using the REDCap e-consent module. REDCap is a secure web application for building and managing online surveys and databases. While REDCap can be used to collect virtually any type of data (including 21 CFR Part 22, FISMA, and HIPAA-compliant environments), it is specifically geared to support online or offline data capture for research studies and operations. The CCHMC REDCap team has templates available for research use for eConsenting which includes Consent to be a Research Subject and Authorization to Use or Disclose (Release) Health Information that Identifies You for a Research Study (HIPAA). The REDCap electronic consent format does not accommodate the current CCHMC formatting which includes headers with logos and stamps on each page and will therefore require some modifications. Participants will be sent a link to review and complete the e-consent on their own, however, study team contact information will be available for questions. Participants will only be sent the surveys once the participant has electronically agreed to participate in the study, by checking “Yes, I consent to participate in the study”..

PPCC staff will be consented as a group prior to engaging in VICTORI. A waiver of documentation of informed consent is also requested for PPCC staff as no private identifiable health information will be collected and the purpose of the study is to evaluate the effectiveness of VICTORI to increase HPV vaccination rates in clinic. A study information sheet will be provided and reviewed with participants prior to the session if completed in person. If session occurs remotely, a study information sheet will be implemented using the REDCap e-consent module following procedures described for the physician participants.

Copies of consent forms for staff and physicians will not be submitted to Health Information Management, since these participants are not patients at CCHMC.

Aim 3: Determine modifiable barriers related to HPV vaccine non-completion for future enhancement of VICTORI accordingly.

Before initiating any study procedures, approval from the CCHMC IRB will be obtained. A waiver of informed consent, parental permission, and assent are requested for Aim 3, as data will be limited to chart review in Epic. This portion of the study can be considered exempt from informed consent procedures as it does not involve procedures for which written consent is normally required and is limited to collection of data previously collected.

Additionally, a waiver of HIPAA Privacy rule is requested of research participants' and their parents and guardians' authorization for use of protected health information (PHI) for research purposes. This is requested for the collection of retrospective data as the use of the PHI involves no more than a minimal risk to the privacy of individuals, participants will be assigned a Study ID in the REDCap database instead of using their name, identifying information will not be used in analyses, identifying information will be destroyed at study closeout, and only study team members will have access to the information linking the Study ID to the participant. All information will be stored in a secure study electronic folder and in REDCap. The research could not be conducted without this waiver nor could it be conducted without access to and use of the PHI.

Compensation

Aim 1

Physicians and staff will receive \$50 for their efforts. Staff will also be provided lunch.

Aim 2

Physicians from PPCC will receive \$50 total for their efforts. PPCC physicians will receive \$40 after completing the pre-survey, the self-directed app, the VICTORI session and the immediate-post survey, and \$10 after the 3-month post survey. Staff will receive a \$10 gift card. Physicians from HSNHC will receive \$25 total for their efforts. HSNHC physicians will receive \$15 after completing the pre-survey, the self-directed app, and immediate post-survey and \$10 after the 3 month post survey.

The electronic W-9 and ClinCard receipt templates developed by the REDCap team will be used for physician participants since not all participants will be seen in-person. They will be used for PPCC staff as well if sessions are conducted remotely. These forms are separate from study data forms in REDCap. ClinCards for physicians and gift cards for staff will be delivered to the participants' mailboxes or work locations within one week of participation.

Aim 3

Not applicable

Future Use

This project will be the first to provide data on the effect of deliberate practice using VICTORI to increase HPV vaccine rates. These data will provide the foundation for an R01 application that will evaluate the intervention's effectiveness in a multisite trial. Data will also support the enhancement of VICTORI to address modifiable barriers associated with vaccine series completion. Furthermore, if effective, we plan to incorporate artificial intelligence into the VR design to allow automated functioning without human facilitation to promote future scalability. This work will positively impact public health by determining the effect of deliberate practice principles to train physicians to strongly recommend HPV vaccines, and thus, increasing HPV vaccination rates and decreasing HPV-associated cancers.

Publication

The authors plan to publish and disseminate the curriculum and its evaluation at the conclusion of the study in the appropriate medical education journals, on-line medical education share sites, and national meetings.

References

2. US Department of Health and Human Services, Healthy People 2020. Immunization and infectious diseases. <https://www.healthypeople.gov/2020/topics-objectives/topic/immunization-and-infectious-diseases>.

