We will conduct a retrospective chart review to explore social determinant of health barriers to vaccine series completion from a retrospective chart review of patients who initiated but did not complete the HPV vaccine series during our study. We will identify patients within the cohort at PPCC and Hopple who initiated but did not complete the HPV vaccine series within a 14 month period following a visit with physicians that participated in the Aim 2 portion of the study. For patients under the age of 15 years, the second dose of the HPV vaccine series is to be administered six months following the first dose. We have operationalized HPV vaccine series completion to occur within 14 months as this provides an adequate and pragmatic timeframe for vaccine series completion at a follow-up visit or annual well child visit.

The primary outcome is the proportion of patients within a cohort at PPCC and Hopple who initiated but did not complete the HPV vaccine series within a 14 month period following a visit with physicians that participated in the Aim 2 portion of the study. These data will be obtained from the EPIC electronic medical record of patients who initiated the HPV vaccine series but have yet to complete it. Data will be entered into a REDCap database. The research materials to be obtained from participants are data collected through review of retrospective chart review of the GPC Social Risk Family Questionnaire, demographic data (DOB, age, sex, race, ethnicity, health insurance), visit information, and HPV vaccine dates (see appendix VICTORI Chart Review).

Potential Benefits

Providers who participate in the VICTORI curriculum will obtain additional knowledge on how to appropriately counsel parents that express vaccine hesitancy. The goal is to improve physician-patient communication which results in improved clinical outcomes (less vaccination refusal) for this high-risk population.

Potential Risks

Aim 1: Evaluate VICTORI for acceptability and feasibility

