Design and Measures: Once acceptability of VICTORI has been assessed through Aim 1 and modifications have been finalized, [name] and [name] will undergo fidelity training to ensure uniform usage of the simulation flow sheets and performance rubrics. Minimum passing score (i.e., performance on simulation that results in vaccine acceptance) will be established using the borderline group standard setting method.⁶⁹⁻⁷¹ The borderline group method is a well-established process for evaluating examinees that uses a checklist to assess proficiency when directly observing a performance test. VICTORI will be implemented using the same methods as described in Aim 1 for physicians and staff. VICTORI VR simulation implementation may take place over ZOOM based on the COVID-19 pandemic and institutional guidelines limiting in-person research visits. VICTORI VR simulation implementation sessions will be audio and video recorded. VICTORI's effect will be assessed using a repeated measures pre-post study design with follow-up period. We will collect monthly baseline data on HPV vaccine initiation and completion rates in PPCC for six months prior to implementing VICTORI. In phase I, VICTORI will be administered to resident and attending physicians. We will then collect HPV initiation and completion rates monthly during the time of intervention implementation and for the following six-months. To assess vaccination rates in clinic compared to HPV vaccination, we will also collect influenza, Tetanus, Diphtheria, and Pertussis (Tdap), and meningococcal conjugate (MCV4) vaccine for the six months prior and post VICTORI implementation in PPCC.

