Next, we will implement VICTORI with staff including nurses and medical assistants in groups of up to 15-20 participants (phase II; secondary outcome). These sessions may take place through a technology-based platform to allow for social distancing dependent on the COVID-19 pandemic and institutional guidelines limiting group meetings and in-person research visits. Staff will watch a 5-minute video on evidence-based practices in recommending the HPV vaccine and observe a facilitator and clinician participating in the VICTORI VR simulations, and then engage in a 5-minute debriefing. Staff will complete a brief pre and immediate post survey assessing their perceived benefits and barriers, subjective norms, and positive messaging about the HPV vaccine on paper or via REDCap. We will collect an additional six months of monthly HPV vaccination initiation and completion data, along with influenza, Tdap, and MCV4. We will collect the same vaccination data from the HSNHC over the same study period to serve as a control. The primary outcome will be the increase in the proportion of patients receiving HPV vaccination seen by resident and attending physicians following participation in VICTORI. Additional secondary outcomes, including physicians' behavioral capability, self-efficacy, perceived benefits, perceived barriers, perceived risk, attitudes, subjective norms, and strength of recommendations, as well as staffs' perceived benefits and barriers, subjective norms, and positive messaging will be assessed via validated survey instruments created by [name] and colleagues (see Appendix B and C).^{41,49,72-76} Physicians' strength of recommendation will be self-reported, which is a common method of measuring this construct.³⁰ In addition, this method (self-reported strength of recommendation) is supported as it is positively associated with vaccination rates documented through medical records.⁷⁷ Physician and staff demographics will also be collected to assess for moderation or confounding. Confidentiality of the results will be maintained. All surveys will have unique IDs with one REDCap form, separate from the surveys including their email and ID. Surveys will also be administered through the REDCap Database. Participants will receive a total of 3 emails encouraging survey completion prior to and following completion of VICTORI. Participants will receive a newsletter periodically via email to enhance retention and provide study updates (appendix). Powerpoint slides will be presented in clinic to as a retention tool as well (appendix).

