
Data Analysis: Repeated measures generalized linear mixed-effects regression (GLMER) will be used to test whether vaccine initiation and completion rates of 9 to 17-year-old boys and girls increase in response to VICTORI. Models will include a logit link function to model the binary patient-level response of vaccine initiation (yes/no) and a random subject-specific intercept to account for patient encounters nested within physicians. Our primary outcome, determining the increase in the proportion of patients receiving HPV vaccination seen by resident and attending physicians in response to the intervention will be tested using the GLMER model including fixed-effect terms for study month (i.e., time) and period (pre-intervention vs. post-intervention). A likelihood ratio test (LRT) for period will provide a formal test of whether vaccine initiations increase in response to the intervention. Differences in the trajectory (i.e., change in slopes) of vaccine initiations between pre- and post-intervention periods will be tested by the inclusion of an interaction term for time and group. The inclusion of a random slope for time will be determined based on assessment of model fit. Polynomial terms or restricted cubic splines will be considered to model non-linear associations in vaccine initiation (i.e., capture the possible early intervention effect and subsequent decline). Additional terms as described for resident and attending physicians in phase I will be added to capture changes in the level and slope of vaccine initiation in response to training staff in phase II. Primary analyses will be conducted for

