physicians (resident and attending combined) enrolled in both the pre- and post-intervention periods. *Secondary analyses* will examine the intervention effect on completion rates, for resident and attending physicians separately, and for all physicians and staff combined. GLMER models as described above will also be used to assess whether background rates of vaccine initiation and completion change over the study period in the absence of the intervention at the control site (HSNHC). Additional secondary analyses will focus on identifying potential mediators of the intervention effect on PPCC providers; whether the effect of the intervention is mediated by changes in the strength of vaccine recommendations and relevant theory-based constructs. Stratified analyses and formal testing of interactions will also be used to assess whether the effect of the intervention differs (i.e. effect modification) according to baseline provider characteristics such as age, sex, and attending vs. resident status, as well as patient characteristics (female vs. male patient, age of patient). As discussed, providers at HSNHC will be receiving the self-directed app-based curriculum component of VICTORI though will not participate in VR simulations and thus will not engage in deliberate practice of curricular skills. HSNHC providers survey responses will be compared to PPCC providers to assess for relevant changes in theory-based constructs including physicians' behavioral capability, self-efficacy, perceived benefits, barriers, and risk, as well as attitudes, subjective norms, and strength of recommendations that might occur following participation in the app-based curriculum only. Survey data will be collected before the app-based curriculum, immediately post-curriculum, and three months after the curriculum. This comparison will be conducted using a two-independent sample t-test.

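### Aim 2 tests series completion in six-month calendar windows although dose two falls six months after dose one, so the completion contrasts cannot be read as physician or staff effects

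*Combined protocol and SAP*

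**What the plan says.** **Data windows (Aim 2, Design and Measures).** The plan will "collect monthly baseline data on HPV vaccine initiation and completion rates in PPCC for six months prior to implementing VICTORI". Physicians are trained first (phase I), and the team will then "collect HPV initiation and completion rates monthly during the time of intervention implementation and for the following six-months". Staff are trained next (phase II): "We will collect an additional six months of monthly HPV vaccination initiation and completion data". The length of the implementation periods is not given.

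**Analysis (Aim 2, Data Analysis).** The mixed model is to "test whether vaccine initiation and completion rates of 9 to 17-year-old boys and girls increase in response to VICTORI". Further terms are added to capture "changes in the level and slope of vaccine initiation in response to training staff in phase II". Secondary analyses "will examine the intervention effect on completion rates", including one for physicians and staff combined.

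**Timing of completion (Protection of Subjects, Aim 3).** For patients under 15, "the second dose of the HPV vaccine series is to be administered six months following the first dose". For Aim 3 only, the protocol adds: "We have operationalized HPV vaccine series completion to occur within 14 months".

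Aim 2 states no denominator for completion, no lag, and no rule that ties a completed series to the period in which it was started.

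**The concern.** Initiation can respond at the visit where the trained physician speaks to the family. Completion of that same series cannot, because the plan's own interval puts it six months later. The phase I window after training is also six months, and staff training comes next. Completions seen in phase I therefore come mainly from series started before training. Those of series that VICTORI prompted appear mainly after staff have been trained, or after data collection stops.

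Two misreadings are at stake. A flat phase I completion result could be taken to mean that physician training does not lead to completed series. A later rise could be credited to staff training when it is the delayed result of extra initiations in phase I.

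**Working it through.** **Inputs from the documents.** Six-month dose interval and 14-month completion window (Protection of Subjects, Aim 3). Windows of 6 months, implementation plus 6 months, and 6 months (Aim 2, Design and Measures). Control-site data to month 22 (Protection of Subjects, Aim 2). Baseline initiation 43%, OR 1.5, 70 physicians, four encounters a month, intercept SD 0.55, power 80% (Power considerations). FY17 counts (Aim 2, Setting and Population).

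**Assumptions.** Physician training builds up linearly over D months, and extra series start in proportion to the share trained. Staff training follows the six-month window at once and takes no time unless stated. A constant share of initiators completes. Dose-two lag is exactly 6 months, uniform over 6–8, or uniform over 6–14.

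**1. The plan's own figure.** Odds 0.43/0.57 = 0.754; × 1.5 = 1.132; probability 1.132/2.132 = 53.1%, as stated. With 70 × 4 encounters over 6 + 6 months, month and period terms, and a two-sided 5% test (assumed, since no alpha is given), power is 79.8% analytically and 79.2% in 600 simulations, against the stated 80%. This concerns initiation; completion has no power figure.

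**2. How many series the six-month interval covers.** FY17 initiations at ages 11–12 were 257 + 289 = 546 of 619 at ages 11–17, so at least 546/619 = 88%.

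**3. VICTORI-prompted series that can complete before staff training.** The ramp contributes D/2 month-equivalents of extra starts and the post-training window contributes 6. With dose two at exactly six months, only the ramp starts complete in time: share = (D/2)/(D/2 + 6) = D/(D + 12). The two right-hand columns were simulated.

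| D (months) | lag exactly 6 | lag 6–8 | lag 6–14 |
|---|---|---|---|
| 0 | 0% | 0% | 0% |
| 1 | 8% | 1% | 0.3% |
| 3 | 20% | 10% | 2.5% |
| 6 | 33% | 24% | 8% |

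If baseline collection starts with the study, 22 − (6 + 6 + 6) = 4 months remain for all training, which caps the best case near 4/16 = 25%.

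**4. Step in monthly completions with no staff effect.** Take D = 0 and initiation rising from 43% to 53%. In phase I no completion yet comes from the higher rate, so the ratio to baseline is 1.00 (simulated 0.998–1.002). In phase II let F be the average share of completions that come from post-training starts. The ratio to phase I is then 1 + F × (53/43 − 1) = 1 + 0.233F.

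| Lag | F | Formula | Simulated |
|---|---|---|---|
| exactly 6 | 1 | 1.23 | 1.232 |
| 6–8 | 5/6 | 1.19 | 1.193 |
| 6–14 | 3/8 | 1.09 | 1.084 |

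The rise is about 8–23%. The small gap in the last row is simulation error.

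**5. Dose-two dates after data end.** For series started in the six months after training the share is 1 − F: 0%, 17% and about 63%. If staff training itself takes three months, the last figure falls to 26%.

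**6. Effect of the denominator.** If only visits with a dose due are modelled, the extra initiators multiply completions and due visits by the same factor, so the rate does not move.

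**The case against.** The strongest reply is that the false staff effect is an inference. The phase II level and slope terms are written for initiation, and no staff-only contrast is specified for completion. The step also depends on an unstated denominator: among visits where a dose is due, it disappears (step 6). Both points stand, and the conclusion is conditional for that reason.

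The phase I contrast is also not empty. Trained physicians see patients whose next dose is already due, so it can show whether they finish series already begun. That stands too. What the contrast cannot show is completion of series started after training ends.

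Two further defences do not succeed. The control site receives the app component only, so it has no VR-driven rise in initiation and no lagged rise to subtract; its models are described as a check on background rates. A smooth time term or spline does not help either, because the lagged rise begins where the phase II terms begin.

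A reader might infer that every VICTORI-started series completes in the staff window, or that the staff effect on completion is biased upward by 23%. The documents support neither. Data are also collected during implementation, so some series can complete in phase I. Slower ones fall after data end. And 23% is the upper end, for dose two at exactly six months.

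**Conclusion.** The concern holds in conditional form. The mismatch between dose interval and window is in the stated design and is not merely missing detail: a series started after physician training ends cannot complete in the phase I window, and at most 0–33% of VICTORI-prompted series can do so for ramps of 0–6 months. With a per-visit or count outcome, the phase I completion contrast is pulled toward null. If the phase II terms are carried over to completion, a rise of about 8–23% would appear with no staff effect.

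These sizes rest on the powered effect, the assumed ramps and lags, and staff training directly after phase I. The 8–23% further assumes immediate physician training. The six-month interval is stated for patients under 15; the Aim 3 analysis mentions three-dose series but gives no interval for them.

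A reader might also infer that the trial's main result is compromised. It is not: completion is secondary, and the primary initiation test and its power are unaffected. The change should be made, but it is not critical.

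**What to change.** 1. Restrict the Aim 2 monthly completion model to visits at which a further dose is due, determined from recorded dose dates, so that more initiations do not by themselves raise the rate. State how due is determined for three-dose series.
2. State that the phase I contrast does not measure completion of VICTORI-started series, and that a calendar-month change in completion during phase II is not evidence of a staff effect. This is needed even after item 1. Table 1 lists the timing of the second dose among the skills taught, and any benefit of that counselling at the dose-one visit would also appear about six months later.
3. Add a supplementary cohort analysis among patients who received dose one: series complete within 14 months (the Aim 3 definition), by period of dose one (before training, after physician training, after staff training) and by initiating physician. State its limit. Pre-period initiators fall due under trained physicians, and post-physician initiators under trained staff. It therefore estimates the effect of training at the dose-one visit and cannot cleanly separate physician from staff effects.

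**Cost.** Items 1 and 2 are analysis-plan wording, using vaccine dates held in the medical record. Item 3 delays the completion readout to 14 months after the last dose one. It also needs extra extraction of dose dates for pre-training initiators, because the Aim 3 cohort (Aim 3, Design and Measures) covers only patients who initiated after seeing a trained provider.
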